3.0 BACKGROUND AND JUSTIFICATION FOR CLINICAL STUDY

Atrial fibrillation (AF) is the most common sustained heart rhythm disorder¹. During AF there are multiple simultaneous waves of contractions, which spread in a chaotic manner through both atria. This arrhythmia results in rapid, uncoordinated contractions, which decrease the blood pumped through the atria. The loss of mechanical efficiency during AF leads to insufficient contractions in the left atrium (LA)². Stagnation of blood flow in the LA leads to hypercoagulability and thus increases the risk for thrombus formation in the LA or left atrial appendage (LAA). Approximately 90% of all the thrombi in subjects with non-valvular AF (NVAF) forming in the LA originate in the left atrial appendage³. The thrombus formation, in turn exposes the patient to thromboembolic events.

Echocardiographic risk factors for LAA thrombus formation include echocardiographic evidence of decreased LAA flow velocity and spontaneous echo contrast within the left atrium and left atrial appendage^{4,5}. The normal flow pattern of the LAA is the ejection of blood from the appendage following atrial contraction at a velocity greater than 40cm/s². Agmon et al. found that the relative risk reduction of ischemic stroke was 2.6 times greater in patients with LAA flow velocities <20cm/s² than those with higher LAA velocities⁶.

Non-valvular AF patients have been assessed to determine the risk of stroke based on the presence of independent risk factors. In a study by Gage et al. the CHADS₂ index was shown to be a tool to predict the risk of stroke in subjects with AF⁷. The CHADS₂ score assigns one point each for the presence of congestive heart failure, hypertension, age greater than 75 and diabetes mellitus and two points for history of stroke or transient ischemic attack (TIA). The study found that AF patients who were not treated with anti-thrombotic agents had an increased risk of stroke ranging from 1.9% to 18.2% as CHADS₂ scores increase from 0 to 6.

A study by Go et al. reviewed outcome data (11,526 patients) in a large primary care setting and confirmed that thromboembolic risk increases progressively with CHADS₂ score⁸. The study also noted that oral anticoagulation with warfarin reduces the risk of stroke in most patients with the exception of those at lowest risk (CHADS₂ score of zero) and highest risk (CHADS₂>5) for stroke. The more recently developed CHA₂DS₂-VASc risk assessment scheme⁹, which identifies truly low risk subjects, assigns two points to age \geq 75 years and previous stroke, TIA or thromboembolism and one point each to congestive heart failure or left ventricular dysfunction, hypertension, diabetes, vascular disease, age between 65-74 years and female sex. A recent validation¹⁰ of these risk schemes in more than 90,000 patients without oral anticoagulation (OAC) but on aspirin showed annual ischemic stroke rates ranging from 0.6% in CHA₂DS₂-VASc = 1 to 4.8% in CHA₂DS₂-VASc = 4, and more than 12% for CHA₂DS₂-VASc = 9.

Clinical Investigational Plan

In a meta-analysis conducted by Andersen et al., warfarin was found to be superior to aspirin and placebo in reducing the risk of systemic embolism in subjects with NVAF¹¹. Hart et al. reported that adjusted dose warfarin reduces stroke risk by 64% (6 trials) and antiplatelet agents reduce stroke risk by 22%¹². The study also reported that risk of intracranial hemorrhage was doubled with adjusted-dose warfarin compared with aspirin.

Recently, new drugs (known as novel oral anticoagulant, or NOAC) have been developed with less dietary and pharmacological interactions than warfarin and less stringent requirements for frequent INR monitoring. Major trials such as RE-LY and ROCKET AF demonstrated that dabigatran and rivaroxaban are non-inferior to warfarin in the prevention of stroke or systemic embolism^{13, 14}. The ARISTOTLE trial demonstrated apixaban was superior to warfarin in preventing stroke or systemic embolism, caused less bleeding, and resulted in lower mortality in subjects with atrial fibrillation¹⁵. The ENGAGE AF-TIMI¹⁶ trial demonstrated both once daily dose regimens of edoxaban were noninferior to warfarin with respect to the preventions of stroke or systemic embolism and were associated with significantly lower rates of bleeding and death from cardiovascular causes¹⁷. A number of characteristics that increase a patient's risk for stroke also increase the patient's risk for bleeding, therefore an alternative to warfarin and NOAC drugs is needed.

Left atrial appendage occlusion (LAAO) is considered a viable alternative to oral anticoagulation (OAC) therapy for stroke prevention in patients with NVAF¹⁵⁻²⁵. Published evidence supporting LAAO is provided in large part by the major randomized controlled trials PROTECT AF and PREVAIL¹⁵⁻¹⁸. Five-year results of PROTECT AF showed superiority of the WATCHMAN™ device in mortality and stroke reduction compared to optimal medical treatment with warfarin¹⁸.

AMPLATZER™ Cardiac Plug device

The ACP device (St Jude Medical, St. Paul, MN, USA) is a self-expandable nitinol device, with fixation anchors. The ACP device is a first generation device based on AMPLATZER occluder technology specifically designed for LAAO.

The AMPLATZER Cardiac Plug demonstrated favorable feasibility and safety in observational studies in Europe²⁶⁻²⁸. Additionally, Park et al. reported the results of an investigator-initiated retrospective study to report on the initial European experience in patients treated with the AMPLATZER Cardiac Plug device between December 2008 and November 2009. SJM's AMPLATZER Cardiac Plug Registry results were also presented at EURO PCR in 2012 and 2014²⁹⁻³⁰. In addition, results from a multicenter study involving 22 sites and 1047 consecutive patients undergoing implant of the AMPLATZER Cardiac Plug device showed a high procedural success rate and a favorable outcome for the prevention of AF related thromboembolism³¹.

In a comparative study between the AMPLATZER Cardiac Plug and the WATCHMAN devices (40 patients each), Chun et al.³² found the devices to perform similarly. The rate of successful implantation achieved with the ACP device was greater than with the WATCHMAN device (100% vs. 95%) although the difference was not statistically significant. TEE at follow-up revealed a significantly higher incidence of residual peri-device flow (jet > 5 mm) for the WATCHMAN device compared to the ACP device, although this was not associated with an increased incidence of thromboembolic events. This finding is consistent with other reports on the ACP device³³.

Clinical Investigational Plan

In conclusion, percutaneous LAAO devices have emerged as an alternate option for stroke risk reduction in non-valvular AF patients at high risk for stroke or not suitable for long-term oral anticoagulant.

Certificate History

Date	Action
29 September 2015	CFDA license
16 October 2012	CE Mark

4.0 RISKS AND BENEFITS OF THE CLINICAL STUDY

4.1 DESCRIPTION OF SUBJECT POPULATION

The population intended for this study is patients who have NVAF and are contraindicated to long-term oral anticoagulant, or patients who experience stroke or relevant event despite taking warfarin.

4.2 ANTICIPATED CLINICAL BENEFITS

Patients suitable to receive the ACP device should be deemed by their physician to have an appropriate rationale to seek an alternative to pharmacologic therapy such as the inability to tolerate long term OAC. The ACP device is intended to be an alternative when long term OAC therapy is unacceptable. A potential benefit of receiving an LAAO device is avoiding long-term OAC, thereby lowering the risk of bleeding. The close follow-up by subjects' treating physicians is a potential benefit for the subject of participating in this clinical study.

4.3 ANTICIPATED ADVERSE EVENTS AND ADVERSE DEVICE EFFECTS

Anticipated adverse events and adverse device effects may occur during and after the ACP device implant procedure. Adverse event definitions are provided in Section 9 and Appendix G. Refer to IFU for a complete list of potential anticipated adverse events.

4.4 RISKS ASSOCIATED WITH PARTICIPATION IN THE CLINICAL STUDY

Risks associated with participating in this clinical study are expected to be no different from risks associated with undergoing ACP device implant which is a commercially available transcatheter device in China.

4.5 RESIDUAL RISKS ASSOCIATED WITH THE DEVICE

The ACP device is market approved in China where the study will be conducted. The risk profile of the ACP device implant procedure is described in the IFU.

4.6 STEPS THAT WILL BE TAKEN TO CONTROL OR MITIGATE THE RISKS

The Sponsor will select investigators qualified by training and experienced to participate in this study. Participating sites will be selected based upon qualifications of the primary investigator. During the study, sites may be subject to quality assurance audits by the Sponsor (or designee), as well as monitoring visits to assess data integrity and study compliance. Additionally, the study will have an

Clinical Investigational Plan

appointed SJM Clinical Safety team that will review and adjudicate all reported serious adverse events. The SJM Clinical Safety team will advise regarding the safety of study subjects.

4.7 RISK-TO-BENEFIT RATIONALE

Risks associated with participating in this clinical study are no different from risks associated with undergoing LAAO implant with a commercially available transcatheter device. The close follow-up by subjects' treating physicians is a potential benefit for the subject of participating in this clinical study.

5.0 STUDY DESIGN

5.1 PURPOSE

To observe the safety and effectiveness of the AMPLATZER™ Cardiac Plug device in Chinese population indicated for use of AMPLATZER™ Cardiac Plug after its market approval by China FDA (CFDA).

5.2 STUDY DESIGN AND SCOPE

This is a prospective, multi-centre, single arm, post-approval observational study.

5.2.1 Number of subjects required to be included in the study

Approximately 343 subjects will be enrolled at up to 35 sites in China in the study (refer to section 13.0 STATISTICAL CONSIDERATIONS).

5.2.2 Estimated time needed to enroll this subject population

The total study duration is expected to be approximately 7 years, dependent on the rate of enrollment and the regulatory timeline. This study will begin enrolment in Q4 of 2016.

5.2.3 Justification for study design

A single-arm observational study is appropriate to observe the safety and effectiveness of the ACP device in the post-market setting in China. The study includes a short-term safety endpoint, a long-term safety endpoint, and a long-term effectiveness endpoint.

The safety and effectiveness endpoints in this study are consistent with those reported for other studies or publications on left atrial appendage occlusion.

The short-term safety endpoint was chosen to reflect serious procedure-related complications during the implant procedure for the ACP device, resulting in either surgical or endovascular intervention. This endpoint appropriately captures important procedural complications and adequately characterizes the short-term safety profile of the procedure and the device.

The long-term safety endpoint is set at 24 months to capture long-term complications associated with the ACP device. This safety endpoint is based on the recently released EuroIntervention consensus document³⁴ on definitions, endpoints and data collection requirements for left atrial appendage occlusion clinical studies

Clinical Investigational Plan

Finally, the effectiveness endpoint appropriately reflects the occurrence of types of events (ischemic stroke or systemic embolism) that the device is intended to prevent. This endpoint is consistent with other studies and publications on left atrial appendage occlusion.

The performance goals for this study have been established primarily based on publications on the ACP device. Information has also been provided to support these performance goals based on outcomes with the WATCHMAN™ device.

Additional descriptive endpoints have been specified to characterize the mechanism of action of the device (i.e., device closure) and the long-term effects of device implant through 5 years.

5.3 OBJECTIVES

5.3.1 Primary Objectives

- (1) To evaluate short term (0 - 7 days post-procedure) safety of AMPLATZER™ Cardiac Plug implantation in Chinese population.
- (2) To evaluate long term safety of AMPLATZER™ Cardiac Plug implantation in Chinese population through 2 years.
- (3) To evaluate effectiveness of AMPLATZER™ Cardiac Plug implantation in Chinese population through 2 years.

5.3.2 Additional Objectives

- (1) To evaluate the occurrence of ischemic stroke or systemic embolism through 5 years in Chinese population implanted with AMPLATZER™ Cardiac Plug
- (2) To evaluate long term safety of AMPLATZER™ Cardiac Plug implantation in Chinese population through 5 years
- (3) To evaluate the immediate successful implantation rate of the AMPLATZER™ Cardiac Plug in the left atrial appendage (LAA)

5.4 ENDPOINTS

5.4.1 Primary Endpoints

1. Short Term Safety

Major adverse events within 7 days after the procedure: short term occurrence of death, stroke (ischemic or haemorrhagic), systemic embolism or procedure or device-related complications requiring major cardiovascular or endovascular intervention.

2. Long Term Safety

The 2-year occurrence of device embolization, device erosion, clinically significant device interference with surrounding structure, device thrombus, device fracture, device infection (endocarditis and pericarditis), device perforation, device laceration, or device allergy.

3. Effectiveness

The 2-year rate of the composite of Ischemic stroke or systemic embolism

Clinical Investigational Plan

5.4.2 Descriptive Endpoints

1. Rate of ischemic stroke or systemic embolism through 5 years post-implant
2. Occurrence of composite of damage to blood vessel or organ or damage to adjacent organs at implant, device dislodgement, device fracture, device erosion, or pericardial tamponade through 5 years post-procedure
3. Device success rate- defined as device deployed and implanted in correct position
4. Rate of closure of the LAA - defined as residual jet around the device of ≤ 5mm, based on the 45-day TEE

5.5 INCLUSION AND EXCLUSION CRITERIA

A subject, who meets all of the inclusion criteria, and none of the exclusion criteria, is eligible to participate in this study.

All subjects enrolled in the study (including those withdrawn from the clinical study or lost to follow-up) will be accounted for and documented, assigning an identification number linked to their names, alternative identification or contact information.

This log will be kept up to date throughout the clinical study by the principal investigator or his/her authorized designee. To ensure subject privacy and confidentiality of data this log must be maintained throughout the clinical study at the clinical site.

5.5.1 Inclusion Criteria

To participate in this clinical subject, the subject must meet all of the following inclusion criteria:

- Patient who meets the current indications and per physician discretion for ACP implant
- Patient who is ≥ 18 years of age at the time of enrolment
- Patient who is able to provide written Informed Consent prior to any study related procedures.

5.5.2 Exclusion Criteria

Subjects are not eligible for clinical study participation if they meet any of the following exclusion criteria:

- Patient who is unable to comply with the follow-up schedule.
- Patient with the presence of intracardiac thrombus
- Patient with active endocarditis or other infections producing bacteraemia
- Patient who has low risk of stroke (CHA2DS2-VASC score is 0 or 1) or low risk of bleeding (HAS-BLED score<3)
- Patient where placement of the device would interfere with any intracardiac or intravascular structures
- Patient who is under medical conditions not appropriate to participate in the study in the opinion of the investigator.
- Patient with LAA anatomy that does not accommodate a device per the sizing guidelines
- Patient who has a life expectancy of less than 2 years due to any condition

Clinical Investigational Plan

- Patient who are currently participating in a clinical investigation that includes an active treatment arm
- Patient who already had a left atrial appendage closure device implanted prior to the study

5.6 INFORMED CONSENT PROCESS

Prior to enrolling in the clinical study and conducting device implant procedure, all subjects will be consented, as required by applicable regulations and the site's IRB/EC. Informed consent must be obtained from each subject prior to device implant procedure. The consent form must be signed and dated by the subject and by the person obtaining the consent.

The principal investigator or his/her authorized designee will conduct the Informed Consent Process. This process will include a verbal discussion with the subject on all aspects of the clinical study that are relevant to the subject's decision to participate in the clinical study.

The subject shall be provided with the informed consent form that is written in a language that is understandable to the subject and has been approved by the center's IRB/EC. Failure to obtain informed consent from a subject prior to study enrollment should be reported to St. Jude Medical within 5 working days and to the site's IRB/EC/ consistent with the site's IRB/EC reporting requirements.

6.0 DEVICE

6.1 DEVICE DESCRIPTION

AMPLATZER™ Cardiac Plug (**Figure 1**) is a transcatheter, self-expanding device intended for use in preventing thrombus embolization from the left atrial appendage. The device is constructed from a nitinol mesh and consists of a lobe and a disc connected by a central waist. The device is designed to facilitate occlusion. The lobe has stabilizing wires to improve device placement and retention. The device has threaded screw attachments at each end for connection to the delivery and loading cables. The device has radiopaque markers at each end and at the stabilizing wires.

The ACP device is recommended for use with the AMPLATZER TorqVue® 45° x 45° Delivery Sheath.

Refer to the Figure1 and Table 1 as below and IFU for more information about the device.

Clinical Investigational Plan

Figure 1: The ACP device and key components

- A. Screw attachments
- B. Waist of device
- C. Lobe
- D. Marker Bands
- E. Stabilizing wires
- F. Platinum thread
- G. Disc

[figure not shown]

Table 1: Model numbers and key dimensions of the ACP device and delivery system

Part Number	ACP Lobe/ Device Size	Left Atrial Disc Size (mm)	Lobe Length (mm)	TorqVue Delivery System
9-ACP-007-016	16mm	20	6.5	9F
9-ACP-007-018	18mm	22	6.5	10F
9-ACP-007-020	20mm	24	6.5	10F
9-ACP-007-022	22mm	26	6.5	10F
9-ACP-007-024	24mm	30	6.5	13F
9-ACP-007-026	26mm	32	6.5	13F
9-ACP-007-028	28mm	34	6.5	13F
9-ACP-007-030	30mm	36	6.5	13F

6.2 DEVICE ACCOUNTABILITY (if applicable)

The ACP device has been approved by CFDA and is commercially released in China. Therefore, there are no additional tracking requirements for this study. Information regarding opened, introduced, and implanted devices will be recorded in the Procedure eCRF and out of service eCRF in case of explant.

6.3 DEVICE HANDLING AND STORAGE

Please refer to IFU.

7.0 PROCEDURES

This study will be conducted in accordance with the clinical protocol and IFU. All persons participating in the conduct of the study will be qualified by education, training, or experience to perform study-related tasks.

The study will not commence until SJM receives written approval from the EC and relevant regulatory authorities, and all required documents have been collected from the participating sites.

Figure 2 below describes the study flowchart for subject screening, consent, enrollment and follow-up through the 5-year follow-up visit. **Table 2** below outlines the testing and assessments required per study visit interval for subjects who are implanted with an ACP device. **Table 3** below outlines the eCRFs to be completed for subjects and as per the recommended study visit intervals.

[figure not shown]
**Clinical Investigational Plan**

Figure 2: Study flowchart for subject screening, consent, enrollment and follow-up

**Clinical Investigational Plan****Table 2: Study visits and activities**

Study Activities \ Visits	Screening & Enrollment & Baseline	Procedure	Post-Procedure/ Pre-Discharge	45 days (+ 45 days)	6M (+/- 3 weeks)	12M, 24M (+/- 6 weeks)	36M, 48M and 60M (+/- 6 weeks, Phone contact)	Interim/ unscheduled Follow-up
Informed Consent Process	X							
- Physical examination - Cardiovascular and medical history - CHA ₂ DS ₂ -VASc score - HAS-BLED score	X							
12-lead ECG	X							
Medication ³ Assessment	X	X	X	X	X	X	X	X
Angiography		X						
TTE			X					
TEE	X ¹	X		X				X ²
Neuroimaging (brain MRI or CT scan)	X ⁴							
Modified Rankin Scale	X							X ⁵
Adverse Event Assessment		X	X	X	X	X	X	X

¹The Baseline TEE is optional if a TEE is performed on the day of procedure to rule out the presence of intracardiac thrombus (including left atrial appendage thrombus) and to assess the size and shape of the LAA. If an exclusion is noted on the TEE and the procedure does not occur, the patient is not enrolled.

²If stroke or TIA is confirmed, complete TEE within 14 days after the awareness of the event.

³Assessment for antithrombotic medication

⁴Neuroimaging can be performed any time from 2 months prior to implant

⁵Perform modified Rankin Scale assessment 90 days after a confirmed stroke or TIA

Table 3: Study visits and electronic case report forms

Visits \ eCRF	Screening & Enrollment & Baseline	Procedure	Post-Procedure/ Pre-Discharge	45 days	6M	12M and 24M	36M, 48M and 60M	Interim/ unscheduled Follow-up
Baseline	X							
Screening	X*							
Procedure		X						

**Clinical Investigational Plan**

Visits eCRF	Screening &Enrollment & Baseline	Procedure	Post- Procedure/ Pre- Discharge	45 days	6M	12M and 24M	36M, 48M and 60M	Interim/ unscheduled Follow-up
Follow Up			X	X	X	X	X	X**
Medication	X		X	X	X	X	X	X**

*for screening failure subject, only screening eCRF is required to be completed.

**Complete if stroke or TIA is confirmed

Additional eCRFs, reports and assessment noted below should be completed upon occurrence, and/or as applicable:

- Withdrawal eCRF
- Adverse Event eCRF
- Protocol Deviation eCRF
- Death eCRF
- Out of service eCRF
- Modified Rankin Scale (Appendix H) (complete 90 days after confirmed stroke or TIA)

If a stroke/TIA is suspected, the subject should be seen by a stroke neurologist for evaluation and appropriate neurological testing (i.e. CT or MRI, and CTA or MRA). If a stroke or TIA is confirmed, the modified Rankin Scale eCRF should be completed 90 days after the event and a TEE is required within 14 days from the date the site becomes aware of the event to confirm device placement, LAA flow parameters and presence/absence of device-related thrombus.

7.1 SCREENING & ENROLLMENT & BASELINE VISIT

The following baseline and enrollment activities are performed as part of the screening process:

- Informed consent process
- Physical examination
- Cardiovascular and medical History
- CHA₂DS₂-VASc score

CHA₂DS₂-VASc	Score
Congestive heart failure/LV dysfunction	1
Hypertension	1
Age \geq 75	2
Diabetes mellitus	1
Stroke/TIA/TE	2
Vascular disease [prior myocardial infarction, peripheral artery disease or aortic plaque]	1
Age 65-74	1
Sex category [i.e. female gender]	1

- HAS-BLED score:

HAS-BLED	Score
Hypertension history (uncontrolled, > 160 mmHg systolic)	1
Abnormal renal function/renal disease (dialysis transplant, creatinine > 2.6 mg/dL or > 200 μ mol/L)	1

Clinical Investigational Plan

Liver disease (cirrhosis, bilirubin > 2x normal AST/ALT/AP > 3x normal)	1
Stroke history	1
Bleeding, anemia, or predisposition to bleeding	1
Labile INR (Unstable/high INR's, or poor time (< 60% time in therapeutic range)	1
Elderly - Age \geq 65 years	1
Drugs - Medication usage predisposing to bleeding (antiplatelet agents, NSAIDs)	1
Alcohol usage history (> 8 drinks/week)	1

- 12-lead ECG
- TEE (optional if a TEE is performed on the day of procedure)
- Antithrombotic medication assessment
- Neuroimaging (brain MRI or CT scan)
- Modified Rankin Scale

The principal investigators or delegated study personnel are responsible for screening all potential subjects to determine subject eligibility for the study. If a subject does not meet all inclusion criteria or meets any of the exclusion criteria, the subject cannot participate in the study and cannot be enrolled. The subject is enrolled in the study when consent has been obtained and the dilator/delivery system is introduced.

Enrollment information (name of the study, date of consent and enrollment criteria, etc.) will be recorded in the hospital records and eCRF. Complete and submit the screening eCRF in a timely manner (recommended within 5 days). Notification of enrollment to the sponsor will take place only when the sponsor receives the Screening eCRF form.

The following terms will be used to describe potential study participants who do not fully implement the study:

- **Consented Screen Failure** - Subjects who sign the Informed Consent Form but do not meet the eligibility criteria. These subjects will not be considered enrolled in the study. Document the enrollment information (name of the study, date of consent and enrollment criteria, etc.) in the hospital records; complete the Screening form.
- **Enrolled Subject – Unsuccessful implant** - Subjects are enrolled but the device was not implanted. The subject will be withdrawn 7 days after procedure. Document the enrollment information (name of the study, date of consent and enrollment criteria, etc.) in the hospital records; The Baseline, Screening, Procedure, Out of service and Withdrawal eCRFs should be completed (withdrawal should occur at least 7 days after the attempted procedure).

Adverse events will be reported from the time the dilator/device delivery system has been introduced to the time the subject concludes the study. An Adverse Event eCRF should be completed, as applicable.

Clinical Investigational Plan

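### The two creatinine limits in the HAS-BLED renal item are not equivalent (2.6 mg/dL is about 230 µmol/L, not 200), which can decide the HAS-BLED <3 exclusion for a narrow group of patients

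*Combined protocol and SAP*

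**What the plan says.** Section 7.1 of the combined protocol and SAP contains the HAS-BLED scoring table. The line that gives one renal point opens "Abnormal renal function/renal disease (dialysis transplant, creatinine > 2.6 mg/dL", and its creatinine limits read "creatinine > 2.6 mg/dL or > 200" µmol/L. Dialysis and transplant earn the same point whatever the creatinine.

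The score feeds an eligibility rule. Section 5.5.2 excludes patients with "low risk of bleeding (HAS-BLED score<3"), and the synopsis repeats the rule. Section 7.1 gives the consequence: anyone who "meets any of the exclusion criteria, the subject cannot participate in the study and cannot be enrolled".

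The visible text does not say which unit governs, whether a laboratory value must be converted before scoring, or which unit the sites' laboratories use.

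**The concern.** A pair of limits for one analyte in two units is normally one threshold printed twice. Here the two numbers look too far apart for that. If they differ, there is a band of creatinine values that passes one limit and not the other. The renal point for a patient in that band then depends on how the line is applied: both limits after conversion, or only the limit printed in the unit of the laboratory report.

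The table is operational, because one point separates a score of 2 (excluded) from a score of 3 (not excluded by this criterion). Section 8.2 uses failure to follow the inclusion and exclusion criteria as its example of non-compliance that may count as a failure to protect subjects. The boundary of the criterion should therefore leave no room for two answers.

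**Working it through.** **Inputs.**
- Conventional-unit limit: above 2.6 mg/dL (section 7.1, HAS-BLED table).
- SI-unit limit: above 200 µmol/L (same line).
- Eligibility rule: a HAS-BLED score below 3 is excluded (section 5.5.2 and synopsis).
- Conversion factor: not in the documents. I take the molar mass of creatinine as 113.12 g/mol, a physical constant, and vary it from 113.0 to 113.2.

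**Step 1. Conversion factor.** µmol/L = mg/dL × 10,000 / molar mass. With 113.12 the factor is 10,000 / 113.12 = 88.4 µmol/L per mg/dL.

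**Step 2. Try to reproduce the printed pair.**
- 2.6 × 88.4 = 229.8 µmol/L (229.7 to 230.1 over the molar-mass range). The plan prints 200.
- 200 / 88.4 = 2.26 mg/dL (also 2.26 at both ends of the range). The plan prints 2.6.
- Gap: 229.8 − 200 = 29.8 µmol/L, and 29.8 / 200 = 14.9%. In the other unit, 2.60 − 2.26 = 0.34 mg/dL.

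The pair does not reproduce.

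**Step 3. Could rounding explain it?**
- If 2.6 stands for anything from 2.55 to 2.65 mg/dL, the SI equivalent runs from 225 to 234 µmol/L.
- If 200 stands for anything from 195 to 205 µmol/L, the conventional equivalent runs from 2.21 to 2.32 mg/dL.

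Neither range reaches the other printed limit, so rounding is not the cause.

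**Step 4. Effect on the score.** Take a patient with no dialysis or transplant and exactly 2 points from the other items.

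| Creatinine, µmol/L | mg/dL | Score, both limits applied after conversion | Score, 200 µmol/L limit only | Score, 2.6 mg/dL limit only |
|---|---|---|---|---|
| 200 | 2.26 | 2 | 2 | 2 |
| 201 | 2.27 | 3 | 3 | 2 |
| 210 | 2.38 | 3 | 3 | 2 |
| 229 | 2.59 | 3 | 3 | 2 |
| 230 | 2.60 (just above the limit) | 3 | 3 | 3 |

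The third and fourth columns agree at every value. Any creatinine above 2.6 mg/dL is already above 200 µmol/L, so under the literal reading the mg/dL limit never changes a score. The last column differs only between 200 and about 230 µmol/L, and always by one point downwards. With 2 other points, that moves the patient from not excluded by this criterion to excluded.

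**Step 5. Where it stops mattering.** With 0 or 1 other points the patient is below 3 either way. With 3 or more, the patient is at 3 or above either way. With dialysis or transplant the renal point is already given.

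**The case against.** The strongest reply is that the line is not ambiguous. It says *or*, so after conversion any creatinine above 200 µmol/L scores, and every patient gets one answer. That is right as a literal reading. It then leaves the 2.6 mg/dL figure with no function, and nothing in the visible text tells a site to convert. A reader holding a mg/dL report would quite naturally compare it with the mg/dL limit and stop there.

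Four stronger conclusions are tempting, and the documents do not support them.

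- *A reader might infer that eligibility actually differs between sites.* That needs sites that report in different units, or that apply the line differently. All sites are in one country and no reporting unit is stated. If every site works in one unit in the same way, no between-site difference arises.
- *A reader might infer that the mg/dL figure is the wrong one.* Being redundant under one reading does not make it wrong. The pair appears only once, with nothing elsewhere to check it against, so the documents show a conflict but not which limit was intended.
- *A reader might want to put a number on the affected subjects.* The documents give no creatinine distribution. The 343 in the plan is also an enrolment figure for subjects who have already passed this criterion, so a share of candidates cannot be applied to it.
- *A reader might infer that baseline HAS-BLED scores are not comparable across sites.* A possible one-point shift in a narrow band does not justify that. The annual reporting list in section 13.2 names baseline characteristics but not HAS-BLED.

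It is also fair to say that nothing in section 13 depends on this. HAS-BLED does not appear in the visible text of the primary hypotheses, performance goals, analysis populations, sample sizes or success criteria.

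**Conclusion.** The line is wrong as written: it gives one creatinine threshold in two units that differ by about 30 µmol/L (0.34 mg/dL, about 15%). The conversion rests only on the molar mass of creatinine, and the result is stable over any plausible value of it.

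The reach is narrow. Eligibility can change only for a patient who meets all of these conditions:
- creatinine above 200 and up to about 230 µmol/L;
- no dialysis or transplant;
- exactly 2 points from the other HAS-BLED items;
- scored at a site that applies the 2.6 mg/dL limit without converting.

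How many patients that is cannot be estimated from the documents; it is probably few. The point merits correction because it sits inside an exclusion criterion, not because it threatens the trial's conclusions.

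**What to change.** The sponsor should reconcile the two limits in the section 7.1 HAS-BLED table: decide which limit is intended, state it once, and give its exact equivalent in the other unit. Any scoring text on the eCRF should be aligned with the result. The choice between the limits is the sponsor's, since the documents do not settle it.

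The cost is one figure in one table and, where the eCRF repeats the limits, the matching text. It adds no patients, visits or tests. Section 15 already allows a written clarification to investigators that is folded into the next amendment, with notification to or approval by the ethics committee and authorities where required. Collecting the creatinine value with its unit would be a larger step, because the baseline schedule in Table 2 lists no laboratory test, and this correction does not need it.
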